While photo documentation decreases cost, compared to 24-hour food recalls, it may have an intervention effect. The possibility exists for the Hawthorne effect (i.e., recording may alter behavior) to cause a decrease in the calories purchased by the control group. However, we anticipate that this will be negligible as adolescents take pictures (e.g., Instagram, snapchat) of things like their food frequently, making it unlikely that the control group will be significantly impacted by submitting pictures of their food purchases.

**Secondary Outcome A** – The number of times the app identifies that users are in a restaurant will be recorded automatically and compared between groups to reveal the program's impact on restaurant visits.

**Secondary Outcome B** – Height and Weight will be obtained at enrollment and post-intervention sessions to determine potential changes in BMI. Though it is likely that use over a longer time will be needed to achieve a statistically significant decrease in BMI, these measures will be obtained to determine if a trend towards a decreased BMI will be demonstrated by the intervention group.

**C.3.a. Population and Recruitment.** We will recruit a total of 150 adolescent/parent dyads from schools, hospitals and places of worship using the methods described above, to participate in the trial, with the goal of recruiting approximately one third of the participants from each of the 3 ethnic groups targeted for this trial. In addition, within each ethnic group we will recruit adolescents in the normal weight, overweight and obese categories (a third each). Recruiting 150 dyads will allow for an expected attrition rate of 20% and still provide the 120 dyads needed to have the power to detect the anticipated changes. Inclusion Criteria: Adolescents 13 – 17 years of age, who eat restaurant food at least 3 times per week, and have a parent who agrees to participate. The RA will contact those who text/call indicating an interest in participation. During the call a baseline enrollment session will be scheduled. Dyads will receive a \$50 gift card at baseline as an incentive for participation and an additional \$50 for each of the two follow-up assessments. A cell phone and payment for data plans will be provided for those who need these in order to participate.

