**C.3.b. Enrollment Session.** Consent/assent will be obtained and height and weight will be measured for adolescents and their participating parents. They will individually complete an online enrollment survey addressing demographics, baseline characteristics, preferences, their level of interest in making dietary changes and any specific changes they wish to make. Adolescent/Parent dyads will download [the LIITAH app](#) and receive instruction in its use and ways to tailor features to their preferences (e.g., graphics, language).

Ame00105576 The focus group part of the study has been completed for both parents and all teens on 9/2020. Due to the COVID-19 situation that hampers physical contact, recruitment for the research study trial (to replace the in-person enrollment sessions due to the COVID situation) will be conducted virtually through UMHealthResearch.org and through a Facebook and Instagram advertising campaign managed by MICHR and linked to our UMHealthResearch study page.

**Randomization:** The technology team will randomly assign dyads as they enroll to either the intervention the control group. They will then adjust the functionality of the app for the participants accordingly, and will send a message to their phone indicating their group assignment, along with instructions for their group.

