### **C.3.c. Six-Week Intervention**

**Baseline Data:** For the first 2 weeks the app will only record presence in a restaurant and ask users to submit photos of their food. In week 3 the program features will be activated for the intervention group.

**Intervention Group:** *Point of Purchase (POP) messages will encourage healthy choices when participants are noted to be in a restaurant.* Participants will be asked to keep the app running on their phone. They will receive a ping when the app identifies that they are in a fast food restaurant followed by a POP prompt, tailored to their preferences and the options available at that location. If they are in a venue without a menu (though this is unlikely as most participants in the developmental project frequented popular franchises with published menus), general healthy suggestions will be provided (such as “consider choosing smaller portions” or “does this venue sell fruit?”). If the app does not ping when they enter a restaurant, they will be asked to register that location by tapping the ‘register location’ button on the app and entering the restaurant name. For detection errors, the appropriate stored venue criteria (location, geo-fence, time of day or dwell time) may be adjusted to improve detection. Users will also be asked to take a picture of any items they buy and to annotate it with information that would help to determine the nutrients in the food. Annotations may be audio, text, or made from a selection of descriptive buttons (e.g., to indicate small, medium or large sizes).

Tailored healthy lifestyle messages will be delivered at times selected by participants. In addition to messages prompting healthy choices at the point of sale, participants will receive tailored messages promoting healthy lifestyle choices. Participants will select the timeframe during which they would like to receive these daily messages. The messages will be tailored to their values, characteristics and preferences, and will address topics such as increased physical activity, obtaining sufficient sleep, and healthy nutrition. As described above, these messages will be based on Self Determination Theory and use motivational interviewing approaches.

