Participants in the intervention group will also be encouraged to use the other features of the app described above (e.g., goal setting, point system, and dyad component). Participants who want a friend use the dyad component will notify the RA at the enrollment session. The RA will obtain assent/consent and provide them with a version of the dyad component that allows them to send encouragement “high fives” to the participant. The friend’s app will only be activated by the tech team if the adolescent is assigned to the intervention group.

**Control Group:** Participants will receive instructions for identification of restaurant locations and submitting annotated photos of their purchases, but they will not receive the other features.

Participants will be contacted as often as once a week by a member of the research team to ensure that the app is working and to answer any questions. We will ask participants if they would like to be recontacted in the future for any additional studies or study-related matters, and if they would like to keep the app on their phones. Participants who had the control version of the app would be able to experience the intervention version of the app.

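### The message that tells dyads their arm has no date, so the text allows them to learn it before or during the two-week record-only baseline; tie it to the week-3 switch.

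*Combined protocol and SAP*

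**What the plan says.** **Assignment (C.3.b, Randomization).** "The technology team will randomly assign dyads as they enroll to either the intervention the control group". The same paragraph continues that the team then sets the app's functionality to match the arm and "will send a message to their phone indicating their group assignment, along with instructions for their group". Neither step has a day or week. Earlier in C.3.b, dyads download the app and are shown how to use it, with no distinction by arm.

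**Baseline (C.3.c, Baseline Data).** "For the first 2 weeks the app will only record presence in a restaurant and ask users to submit photos of their food". Then: "In week 3 the program features will be activated for the intervention group".

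**Other places that bear on disclosure (C.3.c).** If an adolescent nominates a friend, the friend's "app will only be activated by the tech team if the adolescent is assigned to the intervention group"; this is also undated, and it reveals the arm. For controls: "Participants will receive instructions for identification of restaurant locations and submitting annotated photos of their purchases, but they will not receive the other features". For all participants: "Participants will be contacted as often as once a week by a member of the research team to ensure that the app is working".

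**Reactivity (C.3, Primary Outcome).** The plan considers one kind: "The possibility exists for the Hawthorne effect (i.e., recording may alter behavior) to cause a decrease in the calories purchased by the control group". It judges this negligible.

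**Analysis (C.3.e).** Calories purchased are analysed by a linear GEE model with time, treatment and their interaction, and visits by a Poisson GEE model of the same form. The section does not say whether weeks 1-2 enter these models. Pre-post 24-hour recalls are compared between groups among the additional exploratory analyses. BMI change is regressed on initial BMI and treatment.

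No section says that the message is held, or that the arm is concealed during the first 2 weeks.

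**The concern.** The baseline is behavioural and documented by the participants themselves: restaurant visits, and photos of food bought by or for the adolescent. A parent or adolescent who knows that coaching is coming, or that it is not, may buy or photograph differently while the app is still identical in both arms.

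The reactivity that the plan discusses comes from recording, which both arms do. A reaction to knowing the arm differs by arm, so randomisation does not balance it. If weeks 1-2 are in the time-by-treatment model, such a reaction moves the starting point of one trajectory and so changes the estimated interaction. An early fall in the intervention arm hides part of a real effect. An early rise that ends when the features start creates an apparent one.

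The exploratory recall comparison is exposed in the same way if the baseline recalls follow the message. BMI is not, because height and weight are taken at the enrollment session. A comparison restricted to week 3 onward does not use the exposed weeks.

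**Working it through.** **1. What the order of the text allows.**

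| Reading | Supported by | Consequence |
|---|---|---|
| Message at or soon after enrollment | In C.3.b the message follows randomisation, which happens at enrollment. The control instructions in C.3.c cover tasks needed from week 1. | Arm known before or during the baseline |
| Message with the week-3 activation | C.3.b puts the message in the same sentence as the arm-specific app adjustment, and C.3.c places activation in week 3. General app instruction is already given at enrollment. | No bias from this source |

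Neither reading is excluded.

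**2. The plan's own power figure (C.3.e, Power).** Inputs: difference 650 kcal/week, SD 1200, two-sided alpha 0.05, 60 per group, t-test, stated power 80%. The noncentral t gives 83.7% at 60 per group; 80% needs 55 per group. The stated figure is therefore conservative, and the difference does not affect this point. Attrition reproduces: 60/0.8 = 75 per group.

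**3. Effect of an early reaction on the planned interaction.** From the plan: 650, 1200, 60 per group, baseline of 2 weeks. Assumed: one value per week; the SD of 1200 applies to each weekly value; exchangeable correlation c = 0.5; the effect is a step of 650 from week 3; and a reaction of r kcal/week occurs in the intervention arm in weeks 1-2 only. Two lengths are used, because the heading of C.3.c says six weeks while C.3 says 3 months: 6 and 13 weekly points.

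Let k be the distance of weeks 1 and 2 below the mean week, summed, and Sxx the sum of squared deviations of week.

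- 6 points: k = 2.5 + 1.5 = 4, Sxx = 17.5
- 13 points: k = 6 + 5 = 11, Sxx = 182

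Size of the slope difference = k(650 - r)/Sxx. SE = sqrt[2 x 1200² x (1 - c)/(60 x Sxx)].

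- SE, 6 points: sqrt(1,440,000/1,050) = 37.0
- SE, 13 points: sqrt(1,440,000/10,920) = 11.5

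The slope shrinks by r/650, so r = 65 is a 10% loss. Against the plan's planning mean of 765 x 2.5 = 1912.5 kcal/week, 65 is 3.4%.

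| | 6 points | 13 points |
|---|---|---|
| Slope, r = 0 | 4 x 650/17.5 = 148.6 | 11 x 650/182 = 39.3 |
| Power, r = 0 | 98% | 93% |
| Slope, early fall of 65 | 4 x 585/17.5 = 133.7 | 11 x 585/182 = 35.4 |
| Power, early fall of 65 | 95% | 87% |
| Spurious slope, early rise of 65, no true effect | 4 x 65/17.5 = 14.9 | 11 x 65/182 = 3.9 |
| False rejection (nominal 5%) | 6.9% | 6.4% |

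**4. Sensitivity to the correlation at r = 65.** For c from 0.3 to 0.7, false rejection is 6.0% to 8.1%. Power stays above 80% except with 13 points and c = 0.3, where it falls from 82% to 74%.

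**5. Where the shift is zero.** It is zero if the message goes out in week 3, if nobody reacts to it, or if only week 3 onward is analysed.

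**The case against.** The strongest reply is that the text favours the harmless reading. If both arms run the same record-only app for 2 weeks, the arm-specific adjustment belongs to week 3, and the message shares a sentence with it. On that view the plan lacks one date and nothing else. This is a fair reading but not a secure one: a team following C.3.b in its stated order would send the message soon after randomising.

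It can also be said that harm needs three things together: early disclosure, a reaction to the label alone, and baseline weeks in the model. That stands. It is why the case rests on the low cost of the change and not on a demonstrated bias.

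Two stronger inferences are tempting. A reader might infer that the plan unmasks dyads before the baseline; the documents do not say so, and they do not say the opposite. A reader might also infer a large loss. With an assumed reaction of 200 kcal/week, the same formulas give power of 79% (6 points) or 66% (13 points), and false rejection of 23% or 18%. But 200 is 31% of the whole 650 target and 10.5% of 1912.5, from knowing the arm alone, and nothing in the documents supports that size. These figures show only that larger reactions do more harm.

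**Conclusion.** The message and the friend-app activation are undated, and no section conceals the arm during the record-only weeks, so early disclosure is possible under the text as written. Whether it would bias the calorie and visit comparisons depends on when the message is really sent, on whether dyads react, and on whether weeks 1-2 enter the GEE models. Direction and size are unknown.

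A reaction of about 3% of planned weekly restaurant calories would do modest damage: a tenth of the slope, 3 to 6 points of power at correlation 0.5, and false rejection of 6% to 7%. That result rests on the assumed weekly SD, correlation, step effect and reaction. The recall comparison that shares the exposure is exploratory. The change is worth making because it removes an avoidable doubt about the trial's behavioural baseline at very little cost.

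**What to change.** Keep randomisation at enrollment, and amend C.3.b to state that:

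- all dyads receive identical recording instructions at the enrollment session. This covers the control-group tasks needed from week 1;
- the arm-specific app adjustment, the assignment message, group-specific instructions and any friend-app activation take place only at the week-3 switch;
- the baseline recalls are scheduled within weeks 1-2 and, where feasible, before the message. A late recall does not delay the switch.

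**Cost.** The technology team must schedule the message and activation dyad by dyad, since enrollment is staggered, and must not share the assignment before week 3. Sample size, analysed population and randomisation are unchanged.

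**Not needed for this fix.** Masking of contact and recall staff would be a separate addition with its own cost. So would deferring randomisation to the end of week 2, which would leave dyads lost early unrandomised. How weeks 1-2 enter the GEE models is a separate gap in C.3.e.

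**Limit.** After week 3 participants know their arm and still report their own purchases; this change does nothing about that.

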### **C.3.c. Six-Week Intervention**

**Baseline Data:** For the first 2 weeks the app will only record presence in a restaurant and ask users to submit photos of their food. In week 3 the program features will be activated for the intervention group.

**Intervention Group:** *Point of Purchase (POP) messages will encourage healthy choices when participants are noted to be in a restaurant.* Participants will be asked to keep the app running on their phone. They will receive a ping when the app identifies that they are in a fast food restaurant followed by a POP prompt, tailored to their preferences and the options available at that location. If they are in a venue without a menu (though this is unlikely as most participants in the developmental project frequented popular franchises with published menus), general healthy suggestions will be provided (such as “consider choosing smaller portions” or “does this venue sell fruit?”). If the app does not ping when they enter a restaurant, they will be asked to register that location by tapping the ‘register location’ button on the app and entering the restaurant name. For detection errors, the appropriate stored venue criteria (location, geo-fence, time of day or dwell time) may be adjusted to improve detection. Users will also be asked to take a picture of any items they buy and to annotate it with information that would help to determine the nutrients in the food. Annotations may be audio, text, or made from a selection of descriptive buttons (e.g., to indicate small, medium or large sizes).

Tailored healthy lifestyle messages will be delivered at times selected by participants. In addition to messages prompting healthy choices at the point of sale, participants will receive tailored messages promoting healthy lifestyle choices. Participants will select the timeframe during which they would like to receive these daily messages. The messages will be tailored to their values, characteristics and preferences, and will address topics such as increased physical activity, obtaining sufficient sleep, and healthy nutrition. As described above, these messages will be based on Self Determination Theory and use motivational interviewing approaches.

Participants in the intervention group will also be encouraged to use the other features of the app described above (e.g., goal setting, point system, and dyad component). Participants who want a friend use the dyad component will notify the RA at the enrollment session. The RA will obtain assent/consent and provide them with a version of the dyad component that allows them to send encouragement “high fives” to the participant. The friend’s app will only be activated by the tech team if the adolescent is assigned to the intervention group.

**Control Group:** Participants will receive instructions for identification of restaurant locations and submitting annotated photos of their purchases, but they will not receive the other features.

Participants will be contacted as often as once a week by a member of the research team to ensure that the app is working and to answer any questions. We will ask participants if they would like to be recontacted in the future for any additional studies or study-related matters, and if they would like to keep the app on their phones. Participants who had the control version of the app would be able to experience the intervention version of the app.

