## **C.3. Trial (Aim 3)**

**Rationale:** We will demonstrate the impact of using LIITAH on decreasing calories purchased from restaurants by adolescents, along with the number of visits to restaurants and the impact on their BMI.

**Overview:** The trial will consist of 2 arms (an intervention and a control arm) over the course of 3 months.

**Intervention Group** – Will receive the full version of the LIITAH app which consists of 5 components that allow 1) Enhanced Location Identification (ELI), 2) Self-report of Nutrients by Annotated Photos (SNAP), 3) delivery of individually and culturally tailored point of purchase (POP) prompts along with tailored messages sent at other times of day (determined by the participant), 4) use of the app in connection with parents, 5) goal setting capacity, and 6) a point system.

**Control Group** – Will receive a version of the app with only the ELI and SNAP components. Thus, it will detect their presence in a restaurant and allow users to document their purchases by submitting annotated photos, but it will not deliver any POP prompts encouraging them to make healthy choices, or messages at other times of day. It will not allow goal setting or assign points. The control parents will receive a version of the app with only the ELI system to detect when they are in an eating venue and the SNAP component so they can submit and annotated photo of any food they purchase from a restaurant for their adolescent.

**Primary Outcome** – Data regarding the number of calories purchased will be calculated based on the photos submitted and the calorie content as listed in the nutrition information from the restaurant. Comparisons will be made between groups to determine the impact of the program on calories purchased. In addition, 24-hour food recalls will be conducted in the baseline week and final week (3 per week) to provide a comparison assessment of caloric intake from restaurants and to explore changes in caloric intake overall.

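### The visits outcome is counted by detection settings and a venue list that may change during the trial, with nothing to ensure that they change alike in both arms

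*Combined protocol and SAP*

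**What the plan says.** Section C.3 defines Secondary Outcome A by what the app detects: "The number of times the app identifies that users are in a restaurant will be recorded automatically and compared between groups".

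Section C.3.c sets a baseline common to both arms: "For the first 2 weeks the app will only record presence in a restaurant". The arms then diverge: "In week 3 the program features will be activated for the intervention group".

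Two instructions follow, both in the Intervention Group text of C.3.c:

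- on missed restaurants, "If the app does not ping when they enter a restaurant, they will be asked to register that location";
- on detection errors, "the appropriate stored venue criteria (location, geo-fence, time of day or dwell time) may be adjusted to improve detection".

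For controls, C.3 says "Will receive a version of the app with only the ELI and SNAP components", and C.3.c says "Participants will receive instructions for identification of restaurant locations and submitting annotated photos of their purchases". Adjustment of their venue criteria is not mentioned. One provision is not limited to an arm: "Participants will be contacted as often as once a week by a member of the research team", to check that the app works.

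Under Randomization in C.3.b, the technology team allocates the dyads and sets each app's functionality, so it knows the arm. C.3.e analyses visits with a GEE Poisson model in time, group and their interaction.

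The plan gives no date after which venue criteria are fixed, no log of changes, no rule on whether user-registered venues enter the count, no recount under constant criteria and no sensitivity analysis for detection. The 24-hour recalls are planned for calories, so visits have no second source.

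**The concern.** If a geofence is widened or a venue added after week 2, a visit that went unrecorded at baseline is recorded in follow-up although behaviour has not changed. Where this happens equally in both arms, it goes into the time term and does no harm to the comparison. Where it happens more in one arm, it goes into the time-by-group term, which carries the treatment effect, and the model cannot tell the two apart.

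The arms have different reasons to report a miss from week 3. A missed detection costs an intervention participant the point-of-purchase prompt; a control has no prompt to lose. In the other direction, C.1 lets intervention adolescents set goals for how often they eat at fast food venues and lets parents see those goals, which is a reason to leave a missed visit unreported. Adjustment may also go either way: it can recover missed visits, or remove false detections of people passing by. The sign of any bias is therefore unknown.

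At stake is whether a difference in recorded visits, or the lack of one, can be read as behaviour. Without a log, the question could not be settled after the trial.

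**Working it through.** **1. The documents' own figure.** Specific Aims states that Phase 1 identified entry to an eating venue 90% of the time. The Phase 1 results report 143 notifications delivered and 129 answered: 129/143 = 0.902. That reproduces 90.2%, but it is a response rate to notifications that were sent. A missed visit sends no notification and is not in the denominator. If the 90% rests on this figure, as seems likely, the documents give no detection sensitivity. All detection rates below are assumptions.

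**2. Formula.** Let s be the share of true visits recorded, by arm (I, C) and period. Recorded mean = true mean × s. With a log link and time coded as baseline versus follow-up,

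observed interaction ratio = true ratio × (s_I,post / s_I,pre) / (s_C,post / s_C,pre).

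**3. Assumed ranges.**

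| Intervention | Control | Spurious ratio | A true 0.80 is seen as |
|---|---|---|---|
| 70% to 90% | 70% to 90% | 1.00 | 0.80 |
| 90% to 95% | stays 90% | 0.95/0.90 = 1.06 | 0.84 |
| 80% to 90% | stays 80% | 0.90/0.80 = 1.13 | 0.90 |
| 70% to 80% | stays 70% | 0.80/0.70 = 1.14 | 0.91 |
| 70% to 90% | stays 70% | 0.90/0.70 = 1.29 | 1.03 |
| 70% to 90% | 70% to 80% | 0.90/0.80 = 1.13 | 0.90 |
| 80% to 90% | 80% to 85% | 0.90/0.85 = 1.06 | 0.85 |
| 90% to 95% | 90% to 92.5% | 0.95/0.925 = 1.03 | 0.82 |
| stays 80% | 80% to 90% | 0.80/0.90 = 0.89 | 0.71 |

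If detection really starts at 90% and controls never improve, gains in the intervention arm cannot push the ratio above 1/0.90 = 1.11.

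**4. Effect on the test.** The GEE Poisson model was simulated with 60 per arm, 2 baseline and 10 follow-up weeks, 3 true visits per week (the entry minimum in C.3.a), gamma frailty with shape 2, exchangeable correlation and 200 runs per scenario. The frailty, the coding of time and the 12-week split are assumptions; the C.3.c heading says six weeks and C.3 says 3 months. Monte Carlo error is at most √(0.5 × 0.5 / 200) = 3.5 percentage points.

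| Detection | Rejection, no true effect | Rejection, true ratio 0.80 |
|---|---|---|
| 70% throughout, both arms | 5% | about 70% |
| 70% to 90%, both arms | 5% | not run |
| 80% to 90%, intervention only | 23% | about 18% |
| 70% to 80%, intervention only | 22% | 13% |
| 70% to 90%, intervention only | about 74% | about 8% |

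**The case against.** The strongest reply is that detection upkeep is probably shared. The wording permits adjustment and does not promise it. It does not say who adjusts, and it does not make a user's report the trigger. Placement under the intervention heading is weak evidence, because the photo request in the same paragraph plainly applies to both arms. Controls have the same location component, their own instructions on identifying restaurants, and the same staff contact. The two baseline weeks allow early corrections before features diverge, and section C.2.c expects the preloaded menus to cover most places where participants eat. All of this stands. It makes unequal change less likely, but it does not rule it out, and the plan has no means of showing afterwards that it did not occur.

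A reader might go further in four ways that the documents do not support:

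- **That the intervention arm alone will be retuned.** This is nowhere stated.
- **That the bias will hide a benefit.** The direction is open, for the reasons given above.
- **That a missed detection costs points.** C.1 awards points for photos, ratings, goals met and parents' healthy choices, not for being detected, and photos are requested for whatever is bought.
- **That recorded calories drift too.** This needs photo submission to depend on detection, which the documents do not settle.

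**Conclusion.** The concern holds as a missing safeguard on one secondary outcome, on which the trial is not powered. The plan lets the visits instrument change after baseline, gives no assurance that the change is equal between arms, and has no analysis that would detect inequality.

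If detection changes equally, the interaction ratio is biased by a factor of 1.00. With assumed intervention-only gains of 5 to 20 percentage points, the factor is about 1.06 to 1.29. It is nearer 1 if controls also improve, and below 1 if controls improve more or if adjustment mainly removes false detections in the intervention arm. These sizes rest on assumed detection rates and on time coded before versus after activation; with a linear time term, the size would also depend on when the changes were made. The finding does not bear on the primary calorie outcome.

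**What to change.** 1. In both the intervention and the control text of C.3.c, state that the procedure for registering a location and adjusting venue criteria is identical in the two arms, that adjustments are decided without regard to arm, and that they are made in the two baseline weeks where possible.
2. Log every added venue and every criteria change with date and arm, and report the numbers by arm.
3. In C.3.e, pre-specify a visits analysis under one fixed detection rule for all weeks in both arms, reported beside the all-venues count. Either drop venues added or changed after baseline from every week, or recompute visits from stored location data under constant criteria, where such data exist.

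The cost is a few sentences, a log and one further analysis. Dropping changed venues needs only the log. Recomputation needs stored location data, and running two sets of geofences in parallel would cost more, since C.1 notes that both operating systems restrict background processes.

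The fixed count has its own weakness. It misses some venues, and C.1 lets adolescents suggest another venue to a parent, so a move to an unlisted restaurant could be misread as a reduction. That is why both counts are needed, and why the fixed count should not replace the all-venues count.
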